7.4.1 Demographic and Baseline Characteristics

Subject data will be pulled from CP007 and will be used as baseline data for CP007A. Data will be summarised with respect to demographic and baseline characteristics by study treatment group.

7.4.2 Efficacy Analysis

In such a study it is expected that missing data will play an important role in the interpretation of any analysis or description of endpoints. Statistical methods will be used to explore the effects of and the nature of any missing information, including specifically the reasons for non-entry to or discontinuation from the study.

7.4.2.1 Primary Analysis

The primary efficacy variable for this study is the mean Combined Score (TRSS/8+AMS).

For the primary efficacy analysis, the data will be summarised and analysed using methods as for study CP007. The analysis will provide a comparison of the mean Combined Score (TRSS/8+AMS) for each treatment group. In addition, 95% Confidence intervals will be used to explore the size and direction of any differences between groups.

The statistical analysis will use covariates as used in CP007, including pooled centre, age group (as randomised), gender, asthma status and baseline score. Additional informative subgroup descriptive analyses may also be performed.

7.4.2.2 Secondary Analysis

Secondary endpoints will be statistically analysed appropriately to address the secondary objectives of the study, including non-parametric methods, where relevant.

7.4.2.2.1 Rhinoconjunctivitis Symptom Scores

The mean TRSS and the mean component scores of the TRSS (nasal and ocular) during the allergy evaluation periods will be analysed and summarised by treatment group.

7.4.2.2.2 Allergy Medication Usage

The mean AMS during the allergy evaluation period will be analysed and summarised by treatment group.

7.4.2.2.3 Concomitant Medication Use

An evaluation of the use of any concomitant medications associated with rhinoconjunctivitis or related conditions will be performed.

7.4.2.2.4 Rhinoconjunctivitis Quality-of-Life Questionnaire

The mean RQLQ score at the end of the allergy evaluation period will be analysed and summarised by treatment group.

7.4.2.2.5 Medical Visits

An evaluation of additional visits to doctors/clinics will be performed.

7.4.2.2.6 Asthma

An evaluation of asthma progression and the number of subjects developing asthma during the study will be performed in separate analyses.

7.4.2.3 Exploratory Analysis

Other endpoints will be analysed appropriately to address the exploratory objectives of the study, including non-parametric methods, where relevant.

7.4.2.3.1 Sleep

The overall and component scores of the PSQI will be summarised descriptively.

7.4.2.3.2 6-Question ACQ

The data for the 6-Question ACQ will be summarised.

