	
third and fourth year in the study will be performed after all subjects have completed each additional year in the study. At each of the statistical analyses performed after one, two, three and four years, there will be no adjustment to the significance level, apart from the Bonferroni-Holm correction (due to multiple treatment comparisons) stated above.
 
Subject data will be pulled from CP007 and will be used as baseline data for CP007A. Data will be summarised with respect to demographic and baseline characteristics, efficacy variables and safety variables. Summary statistics will include the mean, N, standard deviation, median, minimum and maximum values for continuous variables and frequencies and percentages for categorical variables.
 
Where appropriate confidence intervals will be used to explore the size and direction of any changes in variables or differences between groups.
 
For the primary efficacy analysis, the data will be summarised and analysed using methods as for study CP007. The analysis will provide a comparison of the mean Combined Score (TRSS/8+Allergy Medication Score [AMS]) for each treatment group. The data will be analysed using covariates including pooled centre, age group (as randomised), gender, asthma status and baseline score. Additional informative subgroup descriptive analyses may also be performed.
 
Other endpoints will be analysed appropriately to address the secondary objectives of the study, including non-parametric methods, where relevant.
 
Safety data will be analysed descriptively.

Study Sites	Sites previously participating in clinical study CP007 will participate in this study with the exception of countries where fewer than 10 subjects were randomised.
Planned Study Dates Start of clinical phase End of clinical phase	December 2013 June 2019
Duration of the Study	The duration of the study for each subject will be approximately 4 years.

TABLE OF CONTENTS

PROTOCOL SYNOPSIS	6
TABLE OF CONTENTS	10
1.0 INTRODUCTION.....	14
2.0 OBJECTIVES	16
2.1 Primary Objective.....	16
2.2 Secondary Objectives.....	16
2.3 Exploratory Objectives.....	16
3.0 STUDY DESIGN.....	18
3.1 Overall Study Design	18
3.2 Endpoint.....	19
3.2.1 Primary Endpoint.....	19
3.2.2 Secondary Endpoints	19
3.2.3 Exploratory Endpoints.....	20
4.0 STUDY POPULATION	21
4.1 Number of Subjects.....	21
4.2 Inclusion Criteria	21
4.3 Exclusion Criteria	21
4.4 Females of Childbearing Potential	21

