2.3 Exploratory Objectives

- To evaluate the effect of Cat-PAD on changes in asthma control in asthmatic subjects for up to five years after the administration of treatment.
- To evaluate the effect of Cat-PAD on changes in sleep quality in adults using the Pittsburgh Sleep Quality Index (PSQI) for up to five years after the administration of treatment.
- To evaluate the effect of Cat-PAD on changes in productivity using the Work Productivity and Activity Impairment Questionnaire (WPAI:CIQ-AS) for up to five years after the administration of treatment.

- To evaluate the effect of Cat-PAD on symptomatology on unplanned exposure to a cat in normal daily life in subjects who no longer keep a cat for up to five years after the administration of treatment.
- To evaluate the effect of Cat-PAD on health economic outcomes for up to five years after the administration of treatment.

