#### 13.3.2.1. The Pittsburgh Sleep Quality Index (PSQI)

Observed and change from Baseline values for the overall and component scores of the PSQI are to be summarised by descriptive statistics (n, mean, SD, median, minimum and maximum) for each annual Allergy Assessment Period and treatment arm.

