#### 13.3.2.2. 6-Question Asthma Control Questionnaire (ACQ) Score

Observed and change from Baseline values for the ACQ score are to be summarised by descriptive statistics (n, mean, SD, median, minimum and maximum) for each annual Allergy Assessment Period and treatment arm for subjects with a history of asthma as assessed at the Screening visit of the CP007 study.

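### PSQI and ACQ receive only by-arm descriptive tables although the objectives ask for the effect of Cat-PAD on changes; a baseline-adjusted difference from placebo with a CI would be a cheap, low-priority addition

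*Protocol*

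**What the plan says.** **Objectives.** Protocol 2.3 and SAP 2.3 include an objective "To evaluate the effect of Cat-PAD on changes in asthma control in asthmatic subjects" and a parallel one for adult sleep quality measured by the PSQI.

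**Protocol analysis.** Section 7.4.2.3 opens with a general promise: "Other endpoints will be analysed appropriately to address the exploratory objectives of the study". The synopsis (Statistical Analysis) adds "Where appropriate confidence intervals will be used to explore the size and direction of any changes in variables or differences between groups". The specific entries are narrower. For PSQI: "The overall and component scores of the PSQI will be summarised descriptively". For ACQ: "The data for the 6-Question ACQ will be summarised".

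**SAP analysis.** Section 13.3.2.1 says "Observed and change from Baseline values for the overall and component scores of the PSQI are to be summarised by descriptive statistics". Section 13.3.2.2 says "Observed and change from Baseline values for the ACQ score are to be summarised by descriptive statistics", restricted to those whose asthma history was recorded at CP007 Screening. Both give n, mean, SD, median, minimum and maximum by year and arm. Neither gives a difference from placebo, a confidence interval or a baseline-adjusted estimate.

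**What the SAP has elsewhere.**
- Section 6.2 sets a pre-randomisation CP007 Baseline for every efficacy variable in Section 13.3.
- Section 7.1 defines the baseline covariate generically, as the baseline of whichever score is analysed.
- Section 13.2.2.4 gives the RQLQ, another once-a-year questionnaire, an ANCOVA difference with 95% CI.
- Section 13.3.2.4 gives one exploratory endpoint, global symptom severity, a p-value against placebo.
- Section 13.1.2 also specifies a simplified ANCOVA (treatment and baseline only) for subgroups.

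**The concern.** An objective about the effect of a treatment calls for a contrast with placebo and a measure of its precision. Here the reader gets two descriptive tables per score, and the plan does not say which one addresses the objective. The difference between arms in mean change equals the difference in observed means minus the difference in baseline means, so a chance baseline imbalance moves the two contrasts in opposite directions. Without a pre-specified adjusted estimate, the comparison is left to whoever reads the tables, and precision that the baseline could supply is not used. The ACQ summary is the more exposed of the two, because it covers only the asthma subset.

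**Working it through.** **Inputs.** The documents give no SD, effect size or sample size for PSQI or ACQ. Protocol 7.2 concerns the Combined Score only (SD 1.29, difference 0.525, two-sided alpha 0.025). Its power statements reproduce:
- 266 per arm: 0.525 / (1.29 × √(2/266)) − 2.241 = 2.45, power 99.3%
- 130 per arm: 0.525 / (1.29 × √(2/130)) − 2.241 = 1.04, power 85.1%

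These figures do not bear on the point. They only supply plausible arm sizes.

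**Assumptions.** Results are in SD units. Baseline and follow-up SDs are equal, their correlation r is 0.3 to 0.7, baseline is balanced in expectation, and arm sizes are 60, 130 and 266. The documents state no asthma share, so 60 per arm stands in for a smaller subset such as ACQ.

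**Step 1: effect of a given imbalance.** A baseline imbalance d shifts the observed contrast by r × d and the change contrast by (r − 1) × d. For d = 0.25 and r = 0.5 the shifts are +0.125 and −0.125. With 130 per arm the imbalance has SE √(2/130) = 0.124, so 0.25 is about 2 SE, roughly a 4% event counting both directions.

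An illustration with assumed means: baseline 6.0 (placebo) and 6.6 (active), follow-up 5.5 and 5.7.
- Observed difference: 5.7 − 5.5 = +0.2
- Change difference: (5.7 − 6.6) − (5.5 − 6.0) = −0.4
- Adjusted difference at slope 0.5: 0.2 − 0.5 × 0.6 = −0.1

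**Step 2: how often the two contrasts have opposite signs.** Their correlation is √((1 − r)/2). With no true effect, P(opposite signs) = arccos(√((1 − r)/2)) / π, whatever the arm size. With a true effect it comes from the bivariate normal distribution.

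| True effect, n per arm | r = 0.3 | r = 0.5 | r = 0.7 |
|---|---|---|---|
| None, any n | 30% | 33% | 37% |
| 0.2 SD, 60 | 18% | 17% | 16% |
| 0.2 SD, 130 | 9% | 8% | 6% |
| 0.2 SD, 266 | 3% | 2% | 1% |
| 0.4 SD, 130 | 0.4% | 0.1% | 0.1% |

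A simulation at 130 per arm and r = 0.5 gave 33.3% with no effect and 8.2% with 0.2 SD.

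**Step 3: precision.** In units of 2/n, the variance of the contrast is 1 (observed), 2(1 − r) (change) and 1 − r² (ANCOVA).
- ANCOVA against change: (1 + r)/2 = 0.65, 0.75, 0.85, so variance is 15-35% smaller.
- ANCOVA against observed: 1 − r² = 0.91, 0.75, 0.51, so variance is 9-49% smaller.
- At r = 0.5 both ratios are 0.75 and the interval narrows by 1 − √0.75 = 13%. At 130 per arm the SE falls from 0.124 to 0.107.
- The 95% half-width with ANCOVA at r = 0.5 is 0.31 SD at 60 per arm and 0.21 SD at 130 per arm.

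**The case against.** The strongest reply is that nothing here is an error. Both scores are exploratory and touch neither the alpha nor the success criterion. Descriptive reporting is the SAP's usual treatment of exploratory endpoints (WPAI:CIQ-AS, days off, hospital and doctor visits), with global symptom severity the one exception. The objectives speak of changes, and a change table is planned. This reply largely stands, and it sets the priority.

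Several stronger readings are tempting but not supported:
- **No effect can be estimated at all.** The planned n, mean and SD of change by arm give an unadjusted difference and its CI directly. Only a pre-specified, adjusted contrast is absent.
- **The two tables will generally conflict.** Opposite signs are common only near a null effect or in small samples. With 0.4 SD at 130 per arm the chance is at most 0.4%.
- **Optional entry makes the arms imbalanced.** Self-selection does so only if it differs by arm. Subjects are blind to their CP007 treatment (Protocol 5.3), those told it are excluded (Protocol 4.3), and no differential entry is shown. Nor would ANCOVA be sure to remove such an effect; its guarantee is for chance imbalance with a linear slope.
- **The analysis already exists as code.** The SAP specifies a model; it does not say that it has been programmed.

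Two practical cautions also stand. The full primary model includes pooled site, and SAP 7.2 pools only centres with fewer than five subjects. If 30-50% have asthma (an assumption), a five-subject centre holds 5 × 0.3 = 1.5 to 5 × 0.5 = 2.5 ACQ subjects across three arms, too few to support that factor. And PSQI and ACQ collection in CP007 is inferred from the SAP's planned change tables, because the CP007 protocol is not supplied.

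**Conclusion.** The point holds as a low-priority, cheap improvement. The objectives ask for an effect on changes; the plan gives by-arm summaries without a pre-specified baseline-adjusted contrast or CI, using a baseline the SAP itself treats as available. Apparent disagreement between the two tables is a real possibility where the true effect is small or the sample is limited. The precision gain is modest at about 13% of CI width for r = 0.5. All sizes rest on assumed correlations of 0.3 to 0.7, equal SDs and assumed arm sizes, since the documents give none for these scores. A reader might infer that the exploratory plan is invalid or that the main conclusions are at risk. The documents support neither: a descriptive plan is a legitimate choice here, and the primary analysis is untouched.

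**What to change.** Amend SAP 13.3.2.1 and 13.3.2.2, with a matching sentence in the protocol's PSQI and ACQ entries:

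1. Keep the descriptive tables and state that change from Baseline addresses the objective.
2. For total PSQI and the ACQ score, add the LS mean difference of each Cat-PAD arm from Placebo with 95% CI, adjusted for that score's own CP007 Baseline, in subjects who have one.
3. For PSQI, use the SAP 13.1.2 ANCOVA, dropping any covariate that is constant in the analysed subjects (age group, if all are adults).
4. For ACQ, use the simplified ANCOVA in SAP 13.1.2 (treatment and baseline), with the ACQ Baseline in place of Baseline CS.
5. Label the results exploratory, with no significance claim.

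The cost is SAP wording and two further model fits per year, with no new data. This adds 2 scores × 2 contrasts = 4 estimates per annual analysis. The adjusted estimate also loses subjects without a CP007 value, such as those who turned 18 during follow-up and began the PSQI then, so the number analysed should be shown beside it.

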7.4.2.3.1 Work Productivity and Activity Impairment Questionnaire

The overall and component scores of the WPAI:CIQ-AS will be summarised descriptively.

7.4.2.3.2 Global Assessment of Symptom Severity

An evaluation of the global assessment of symptom severity on unplanned exposure to a cat in normal daily life in subjects who no longer keep a cat will be performed.

7.4.2.3.3 Health Economic Outcomes

Health economic outcomes will be described and explored.

7.4.3 Safety Analysis

Safety will be evaluated by analysis of the following parameters:

- AEs;
- SAEs

For safety analysis, frequency distribution will be summarised for categorical variables. No formal inferential tests will be performed on safety data.

The number and percentage of subjects who experience AEs will be presented by treatment group. Based on the MedDRA Preferred Term, subjects who experience the same AE on multiple occasions will be summarised at the maximum severity and most conservative relationship to the study medication. If 2 or more AEs are reported as a single event, the

individual terms will be reported as separate AEs.

The total number of AEs will be summarised by MedDRA System Organ Class and Preferred Term for each treatment group. Descriptive statistics will be presented for differences between each treatment group and the placebo group, but no hypothesis testing is planned.

Any deaths and SAEs and AEs will be summarised by CP007 treatment group.

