2.2 Secondary Objectives

- To evaluate the continued safety and tolerability of Cat-PAD for up to five years after the administration of treatment.
- To evaluate the effect of Cat-PAD on Rhinoconjunctivitis Quality-of-Life Questionnaire (RQLQ) for up to five years after the administration of treatment.
- To evaluate the effect of Cat-PAD on the onset of asthma for up to five years after the administration of treatment.
- To evaluate the effect of Cat-PAD on asthma progression in subjects previously enrolled in CP007 with GINA 1 asthma for up to five years after the administration of treatment.

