## 14. SAFETY OUTCOMES

All outputs for AEs are to be based on the Safety population.

There are to be no statistical comparisons between the treatment arms for safety data, unless otherwise specified with the relevant section.

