#### 14.1.1. ALL AEs

Incidences of AEs are to be presented by System Organ Class (SOC) and Preferred Term (PT) and also broken down further by maximum severity and strongest relationship to study medication.

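### The protocol says differences from placebo in adverse events, and event totals by SOC and PT, will be reported; the SAP specifies neither and gives no reason

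*Protocol*

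**What the plan says.** **Protocol.** Section 2.2 lists safety as a secondary objective: "To evaluate the continued safety and tolerability of Cat-PAD for up to five years after the administration of treatment". Section 6.4.4 makes AEs the only safety parameter. Section 7.4.3 states that "No formal inferential tests will be performed on safety data" and then commits to the number and percentage of subjects with AEs in each group and to two further outputs:

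- Event totals: "The total number of AEs will be summarised by MedDRA System Organ Class and Preferred Term for each treatment group".
- Differences: "Descriptive statistics will be presented for differences between each treatment group and the placebo group, but no hypothesis testing is planned".

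The synopsis says "Safety data will be analysed descriptively".

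**SAP.** Section 14 opens its rules for safety with "There are to be no statistical comparisons between the treatment arms for safety data, unless otherwise specified with the relevant section". The planned outputs are:

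- 14.1: an overall summary with number of subjects, percentage and number of mentions (m) for six categories: any AE, AE by maximum severity, AE by strongest relationship, AE leading to withdrawal, serious AE, and AE leading to death.
- 14.1.1: incidences by SOC and PT, also split by severity and relationship.
- 14.1.2: frequencies and percentages of AEs leading to withdrawal, by SOC and PT.
- 14.1.3 and 14.1.4: a summary by SOC and PT of serious AEs and of AEs leading to death.

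SAP section 1 says that the plan is based on Protocol version 5.

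**The concern.** The protocol separates describing a difference from testing it: it declines the test and keeps the description. The SAP replaces this with a rule about comparisons in general and then specifies no difference of any kind. It also drops the event total at SOC and PT level, where repeated events in the same subject would show.

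The safety groups are the CP007 treatments, including placebo, so the contrast with placebo is the informative quantity for this objective. Percentages shown side by side, without the difference or its uncertainty, invite a reader to take similar figures as evidence of no difference. If the difference is not pre-specified, the choice of which contrasts to show, and on what scale, may be made after unblinded outputs have been seen.

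**Working it through.** The plan gives no safety figure to reproduce, so the main check is a comparison of texts.

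**Step 1. Match each output in Protocol 7.4.3 to the SAP.**

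| Protocol 7.4.3 | SAP 14 to 14.1.4 | Match |
|---|---|---|
| Number and % of subjects with AEs, by group | 14.1, 14.1.1 | Yes |
| Total number of AEs by SOC and PT, by group | m appears in 14.1 by overall category only; 14.1.1 says incidences, a term it does not define | Not specified |
| Descriptive difference from placebo, each group | None in 14.1 to 14.1.4 | Missing |
| No hypothesis tests | 14 | Yes |

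**Step 2. Test the most generous reading of SAP 14.** Suppose that statistical comparisons means only hypothesis tests. SAP 14 then agrees with the protocol, and a descriptive difference is allowed. Even so, no section plans one. The omission stands on either reading.

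**Step 3. Look for a stated reason.** Sections 14 to 14.1.4 give none and do not mention a departure from the protocol.

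**Step 4. Illustrate what a difference with an interval would add.** The documents give no AE rates and no safety sample size. Assumptions:

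- Serious AE rate of about 5% in each arm.
- 469 per arm: the 1408 subjects that SAP 3.1 gives as the maximum, with equal allocation to three arms assumed (1408/3 = 469). This is a ceiling.
- 266 per arm: the evaluable number in the efficacy power statement of Protocol 7.2, used here only as a smaller case.

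With the same observed proportion p in both arms and Wilson limits l and u, the Newcombe half-width is √[(u − p)² + (p − l)²].

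- 23/469 in each arm: p = 4.90%, l = 3.29%, u = 7.25%. √(2.35² + 1.61²) = 2.85 percentage points.
- 13/266 in each arm: p = 4.89%, l = 2.88%, u = 8.18%. √(3.29² + 2.01²) = 3.86 percentage points.

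**Step 5. Vary the assumed rate.** The simple half-width 1.96 × √[2p(1 − p)/n], in percentage points, gives:

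| Assumed rate in both arms | n = 469 | n = 266 |
|---|---|---|
| 1% | 1.3 | 1.7 |
| 5% | 2.8 | 3.7 |
| 10% | 3.8 | 5.1 |
| 50% | 6.4 | 8.5 |

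At 1% fewer than five events per arm are expected (0.01 × 469 = 4.7; 0.01 × 266 = 2.7), so that row is rough.

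**The case against.** Several points on the other side stand.

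- **A reader might infer that the SAP contradicts the protocol by forbidding comparisons.** The wording does not carry that. It concerns statistical comparisons, has an exception clause, and can be read as the protocol's own ban on tests. The defect is an output left out.
- **A reader might infer that the SAP plans only per-arm incidences.** It does not. Section 14.1 counts mentions for every overall category, and the summaries in 14.1.3 and 14.1.4 are not limited to incidences. The gap in counts is at SOC and PT level.
- **A reader might infer that a promised confidence interval was dropped.** Protocol 7.4.3 promises descriptive statistics and names no interval. The synopsis has a general line, "Where appropriate confidence intervals will be used to explore the size and direction of any changes in variables or differences between groups", but it is conditional and not specific to safety. An interval is an improvement to recommend, not an unmet commitment.
- **A reader might want to convert the illustration into a multiple of the placebo risk.** Dividing the limit of a risk difference by the observed placebo rate treats that rate as known without error, so it is not a valid limit for a risk ratio. A per-arm number reduced for withdrawals would not suit either: the safety population is all subjects (SAP 5.4), and AEs are cumulative and not assigned to a year (SAP 4.1).
- **The output shells are not among the documents.** SAP 1, 4.1 and 8 refer to shells and templates. A difference column or an m column might exist there. The finding therefore concerns the SAP text.
- **No information is lost.** Given n and % per arm, anyone can subtract and compute an interval, and no success rule uses safety. This limits the weight of the point. It does not replace pre-specifying an output that the protocol says will be presented.

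**Conclusion.** The concern holds as an unexplained omission. The SAP text specifies no descriptive difference from placebo for AEs and no event totals by SOC and PT, although Protocol 7.4.3 states both, and they serve a secondary objective. This follows from the texts alone and needs no assumption, subject to the unseen shells.

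The practical effect is modest. As an illustration, an observed difference of zero in serious AEs at about 5% would leave an uncertainty of roughly ±2.9 percentage points at the ceiling of 469 per arm and ±3.9 at 266 per arm. These figures rest on the assumed rate and, for 469, on equal allocation and full enrolment. They show why an interval is useful. They do not measure the precision of this study, whose safety numbers are not given.

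**What to change.** 1. In SAP 14, exclude hypothesis tests on safety data instead of statistical comparisons.
2. In SAP 14.1, for the overall AE categories, add the risk difference for each Cat-PAD arm minus Placebo. Recommended addition: a 95% confidence interval, labelled descriptive and unadjusted, with no p-value.
3. In SAP 14.1.1, add the number of events (m) to the SOC and PT table.
4. If the sponsor prefers not to produce these outputs, record the departure from Protocol 7.4.3 in the SAP and justify it.

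The cost is SAP wording and some table columns; no new data are needed. The drawback of the intervals is their number. With one row for each of the six categories there are 6 × 2 = 12. If the three severity and three relationship levels each have a row there are (4 + 3 + 3) × 2 = 20. For that reason the intervals should stay with the overall categories and not be extended to every SOC.
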